## Adjustment for non-compliance/cross-over

We also need to consider dropouts and poor adherence in calculating the sample size. It is estimated that around 5%-8% patients in both groups will drop out in different stages of the trial. The adjusted sample size is calculated based on the following formula –

Adjusted sample size,  $n_{adj} = n/(1-c_1-c_2)^2$ 

Here, n = 270

 $c_1$  = Dropout rate in control group = 8%

c2= Dropout rate in control group = 8%

Adjusted sample size,  $n_{adj} = 270 / (1 - .08 - .08)^2$ 

 $= 384 \approx 400$ 

The adjusted sample size in each group = 200

#### j. Operatinal definition:

#### Rome III criteria for diagnosing IBS

Recurrent abdominal pain or discomfort (an uncomfortable sensation not described as pain) at least three days a month in the past three months, associated with two or more of the following:

- Improvement with defecation.
- Onset associated with a change in frequency of stool.
- Onset associated with a change in form (appearance) of stool.

Criteria should be fulfilled for the past three months with symptom onset at least six months before diagnosis.

IBS patients will be diagnosed by translated and validated enhanced Asian ROME III questionnaires in Bengali language for diagnosis of IBS. (Mohammed et al, 2014).

#### **Outcome variables:**

According to the EMEA Guidance on the Evaluation of Medicinal Products for the Treatment of IBS, a responder is defined as a patient one whose abdominal pain score has improved at least 30 % compared to baseline.

#### **Confounding variables:**

These are the factors that may influence the course of the study and modulate the findings on interpretations.

Following are the confounding variables in this study and these will be addressed accordingly:

[figure not shown]
1. Psychological status- IBS is a functional gastrointestinal disorder and by definition psychological attributes i.e. anxiety and depression may influence the appearance and/or severity of pain and bowel motion. Such patients in this study

[figure not shown]
- will be managed by anxiolytics and the antidepressants in appropriate cases so that their psychological status does not influence the outcome of the study.
- 2. Dietary factors: Some dietary components may aggravate abdominal pain and frequency of bowel motion in IBS. Patient of both groups will be provided with similar dietary advices. So that dietary component can not influence the outcome of the study.
- 3. Drugs: Spasmolytics, antidiarrhoeal and bulk forming agents will be prescribed in both the groups similarly according to the needs of the patients. So that they do not influence the outcome of the study.

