# **Secondary Objectives:**

- To assess the effect of probiotics on global symptom severity scores which includes other symptoms of IBS (stool consistency, frequency, bloating) using a validated symptom severity score.
- 2. To assess changes in the use of rescue medication (i.e. laxatives or anti diarrhea medication such as Loperamide).
- 3. To assess any adverse events reported with probiotic use.

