### c. Main outcome variables to be studied:

Changes in abdominal pain for primary objective and overall symptom severity score as a secondary objective.

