#### d. Checklist of Variables:

Height Weight

BMI DM

Psychological disorder(depression, anxiety)

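### Prescribing symptomatic drugs by need in both groups does not stop them influencing the pain outcome, so the protocol's no-influence statement should go and the result be read as including co-treatment

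*Protocol*

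**What the plan says.** The protocol's section on confounding variables names drugs as a factor that could alter the findings. Its answer in item 3 is that "Spasmolytics, antidiarrhoeal and bulk forming agents will be prescribed in both the groups similarly according to the needs of the patients", followed by "So that they do not influence the outcome of the study". Item 1 deals with anxiety and depression, which it accepts may affect the severity of pain. Such patients "will be managed by anxiolytics and the antidepressants in appropriate cases so that their psychological status does not influence the outcome of the study".

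Other parts of the protocol bear on this:

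- **Outcomes.** Section c gives the outcomes as "Changes in abdominal pain for primary objective and overall symptom severity score as a secondary objective". Under Outcome variables, "a responder is defined as a patient one whose abdominal pain score has improved at least 30 % compared to baseline". Neither mentions other drugs taken.
- **Secondary objective 2.** This is "To assess changes in the use of rescue medication", with laxatives and antidiarrhoeals as the examples.
- **Inclusion criterion 5.** Patients agree not to start another drug, except where clinically indicated.
- **Diary (section on procedures).** It covers concomitant medication taken consistently at a stable dose over two months. Loperamide and laxatives are the drugs named.
- **Analysis (section p).** Symptom scores are compared by an unpaired t-test. No covariate and no handling of co-treatment is stated.
- **Intention to treat (section q).** Patients are analysed as allocated, whatever happens afterwards.

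**The concern.** Item 3 treats a shared prescribing policy as if it produced equal drug use. It does so only if need is equal in the two groups. Need follows from symptoms during the trial, so it is partly a result of treatment. If the probiotic works, control patients will tend to need more symptomatic drugs. Those drugs lower their pain scores, and the observed difference understates what the probiotic does by itself.

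The responder definition counts a 30% improvement whichever drug produced it, and the stated t-test does not separate the sources either. The first primary objective is the effect of the probiotic on abdominal pain. A reader who relies on item 3 would take the observed difference as that effect, with co-treatment ruled out as a contributor. The text gives no ground for that.

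**Working it through.** **The plan's own figures.** Section i uses an SD of 87.77, a difference of 30 (entered as score points), z values of 0.84 and 1.96, and equal groups.

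- n per group = 2 × 87.77² × (0.84 + 1.96)² / 30² = 134.2, or 135 as stated (270 in total).
- Adjusted total = 270 / (1 − 0.08 − 0.08)² = 382.7, against 384 stated, rounded to 400 (200 per group).

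These reproduce closely enough. No planning number is in dispute here.

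**Shift in the mean.** Let e be the excess share of control patients using a symptomatic drug, and R the points by which the drug lowers the score. The observed difference is the probiotic's own difference minus R × e. It is untouched only if R = 0 or e = 0, and item 3 secures neither. The protocol gives no value for R or e, so everything below is assumed.

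*Pain item, 0-100.* With e from 10% to 20% and R from 10 to 20 points:

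- low end: 0.10 × 10 = 1 point
- high end: 0.20 × 20 = 4 points

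The protocol gives no SD for the pain item, so this cannot be turned into power.

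*Total severity score.* Here the protocol does give an SD. With a true difference of 30 and 200 per group, the standard error is 87.77 × √(2/200) = 8.777, and power = Φ(difference / 8.777 − 1.96).

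| Assumed R | Assumed e | Difference left | Power |
|---|---|---|---|
| any | 0 | 30 | 93% |
| 30 | 10% | 27 | 87% |
| 30 | 20% | 24 | 78% |
| 30 | 30% | 21 | 67% |
| 60 | 10% | 24 | 78% |
| 60 | 20% | 18 | 54% |
| 60 | 30% | 12 | 28% |

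*Responders.* With 8% dropout, 200 × 0.92 = 184 per group are evaluable. At two-sided 0.05, 50% versus 35% has 83% power. If co-treatment lifted control responders to 40%, 50% versus 40% has 49% power. All three rates are assumed. They are not derived from the 1 to 4 point shift, and the fall in power simply reflects a gap of 10 points in place of 15.

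**Does another part of the protocol repair the statement?** The as-allocated analysis defines a valid comparison of two strategies but does not equalise drug use. Inclusion criterion 5 limits new drugs but exempts those clinically indicated, which is the needs-based case. The diary, as worded, does not fit drugs started or increased as symptoms change, and it names neither antispasmodics nor psychotropics.

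**The case against.** The strongest reply is that co-treatment belongs to the trial's question. The research question asks whether probiotic with standard treatment is better than standard treatment, both groups receive standard treatment, and patients are analysed as allocated. For that question, drugs given by need are part of each strategy, and randomisation protects the comparison. This stands. A reader might infer that the primary comparison is biased or invalid, and the documents do not support that.

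Four other stronger readings are tempting and also fail:

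- **That the protocol contradicts itself by expecting the probiotic to change rescue use.** Secondary objective 2 only sets out to assess changes. It shows that use is regarded as something that may vary, which sits badly with item 3, but it predicts no difference.
- **That item 1 says psychotropic drugs have no effect on the outcome.** It says that psychological status will have none. The reasoning is weak in a similar way, but the claim is a different one.
- **That co-treatment could create a false benefit.** This needs prescribing to be influenced by knowledge of the arm. It depends on a separate conflict: a double-blind, placebo-controlled title against a control group described as having standard treatment only. Those places must be reconciled in their own right.
- **That the protocol says these drugs are started after randomisation.** This is inferred from prescribing within the two groups; it is not written.

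It is also fair to say that detailed handling of co-treatment may stand in an analysis plan that was not available. That would not cure item 3, because the statement is in the protocol.

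**Conclusion.** The point holds as a wrong statement with a consequence for interpretation. Similar needs-based prescribing does not keep antispasmodics, antidiarrhoeals and bulk-forming agents from influencing pain. Use can differ by arm and can shrink the difference attributable to the probiotic itself. The randomised comparison of the two strategies, co-treatment included, remains sound.

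The size cannot be known from the documents. The 1 to 4 points on the pain item and the power figures rest wholly on assumed differences in use and assumed drug effects. At the low end the shift is small. The correction is worth making before data collection, because use that was not recorded cannot be examined later.

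**What to change.** Prescribing stays with the clinicians. The changes are to wording, analysis and recording:

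1. In item 3, delete the statement that the drugs do not influence the outcome. State that the comparison is of probiotic plus standard treatment with standard treatment, including whatever co-treatment is given.
2. In section p, replace the unadjusted t-test for pain with a comparison adjusted for baseline pain, which is already collected. Add baseline psychological disorder, which is on the variable checklist, if it is recorded at entry. This is for precision and does not cure differences in co-treatment.
3. Pre-specify a sensitivity responder analysis in which a patient who started or increased symptomatic co-treatment before the assessment counts as a non-responder. Tabulate use by arm.

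**Cost.** Step 1 is wording, and adjusting for baseline pain needs no new data. Responder rates in the sensitivity analysis will be lower, and that analysis answers a different question from the main one. The diary is now worded for stable-dose medication with loperamide or laxative named. It must also record new or increased use of the other drug classes. Until it does, step 3 can cover at most the drugs the diary names. Psychological disorder may need an extra line on the data sheet.

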## Follow up schedule:

Participants will be followed up before intervention for baseline information and 1 month interval during treatment including 1 month post treatment.

# k. Flow chart showing the sequence of tasks:

# 1. Procedures of preparing and organizing materials:

In people who meet the IBS diagnostic criteria, the following tests should be undertaken to exclude other diagnoses:

- Full blood count (FBC)
- Erythrocyte sedimentation rate (ESR) or C reactive protein (CRP)
- Antibody testing for coeliac disease
   (Endomysial antibodies [EMA] or tissue transglutaminase [TTG]).

Participants who fulfill the inclusion criteria in the absence of exclusion criteria will be included in the study. IBS patients will be diagnosed by translated and validated enhanced asian ROME III questionnaires in Bengali language for diagnosis of IBS. (Mohammed et al, 2014) Informed written consent will be obtained from participants. Data will be collected in questionnaire.

All the participants are advised to remain on their usual normal diet during the study period. Approximately total of 400 participants will be recruited in this study. They will be divided into two groups by randomization software, consisting of 200 in each group. One group will receive two capsules of probiotics (Bio-Cult, Sandors BD Ltd.) twice daily before or during a meal with standard treatment, while the other group will receive only standard treatment for 8 weeks.

Bio-Cult is a 14 strain probiotic formulation in a capsule form. Two capsules twice a day is equivalent to 8 billion CFUs (2 billion per capsule). The strains are-

[Bacillus subtilis PXN 21, Bifidobacterium spp. (B. bifidum PXN 23, B. breve PXN 25, B. infantis PXN 27,B. longum PXN 30), Lactobacillus spp. (L. acidophilus PXN 35, L. delbrueckii spp. Bulgaricus PXN39, L. casei PXN 37, L. plantarum PXN 47, L. rhamnosus PXN 54, L.helveticus PXN 45,L. salivarius PXN 57) Lactococcus Lactis PXN 63, Streptococcus thermophilus PXN 66].

Changes of symptoms will be assessed by using a previously used validated IBS instrument. (Richard Lea et al.2001). Symptom severity scoring system of IBS is shown in diagram-1 (C.Y. Francis et al. 1997). Symptom severity scores specially for abdominal pain, global symptom severity will be assessed as baseline and at 1 month

interval during treatment along with 1 month post treatment. This scoring will be done

on the basis of monthly interviews.

The collective scores to these individual domains give rise to the total score. The IBS-

SSS total score ranges from 0 to 500; a higher score indicating worse condition.

Scores below 175 represent mild IBS, 175-300 represent moderate severity, and

scores above 300 represent severe IBS.

Patients will be asked to keep a diary with details of use of concomitant medication

provided used consistently over last 2 months with a stable dose i.e. Loperamide or

laxative including amount, frequency and duration.

All data will be recorded in a printed data sheet.

m. Randomization:

Randomization procedure will be done by randomizer software (www.randomizer.org)

n. Equipments to be used:

For data collection: Data collection sheet.

o. Assurance of compliance in trial:

The patient will be motivated for compliance. They will be assessed for willingness

before selection. Adequate information will be provided regarding dose and duration

of drugs. Patient will be followed up monthly for 3 months for improvement and also

for compliance. Compliance will be assessed by counting the foils/boxes of use

medication. Compliance will also assessed by asking about other medications and

dietary patterns of the patient.

20

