# **PROTOCOL**

Supplementation with a multi-strain probiotic formulation (Bio-Kult®) in the management of diarrhoea-predominant irritable bowel syndrome - a randomized, double-blind, placebo-controlled clinical trial

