#### **ABSTRACT**

**Background:** Irritable Bowel Syndrome (IBS) is a common functional gastrointestinal disorder. Common clinical manifestation include abdominal pain, bloating, altered bowel habit which bears a great impact on the quality of life of an individual. Previously limited number of studies carried out in our country to assess the effect of probiotics on IBS patients which yielded mixed results. Further study preferably with larger sample and longer duration was recommended. Aims and objectives: This study aims to see the effect of probiotics on IBS.

Material and method: This is a controlled randomized clinical trial. The patient will be selected on the basis of Rome III criteria. IBS patients with a sample size of 400 will be taken. Purposive non probability method of sampling will be employed. In this method the patients who will be readily available and in close proximity will be selected according to the selection criteria. Patient will be collected from gastroenterology outpatient department. After full explanation of the study procedure, informed written consent will be taken. Participants will be randomized to receive either probiotics (Biocult®, Sandooz Bd. Ltd.) with standard treatment or only standard treatment for 8 weeks. All participants will be interviewed with baseline symptom score. Similar interview for symptom score will take place at 1 month interval for 3 times (including 1 month post treatment). All data will be processed by the SPSS program values will be expressed as frequencies or mean±SD unless otherwise mentioned. Between groups analysis will be done by Chi-square test, unpaired or paired students t-test as applicable; while predictive values will be seen by regression analysis. Only P values <0.05 will be considered as significant.

**Result:** This study will see the effect of two months use of probiotics on IBS and thereby highlight over the longer treatment of IBS.

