defecation or its onset is associated with an increased or decreased frequency of stool or looser or harder stool. The pain often is poorly localized, waxes and wanes, may be aggravated by eating & can occur in any part of abdomen; although it is more typically located in the lower abdomen. It can be referred to different areas in the abdomen or to the chest or back. Exacerbation of pain by stressful life events or difficult life situation is common. As abdominal pain is the hallmark feature of IBS and is recommended for the time being to assess the main symptomatology in at least partially validated scale. So, improvement of abdominal pain or discomfort along with abnormalities in defecation is considered as primary outcome. For other subtypes of IBS, and for "global" development programs intending to treat two or more subtypes, the use of the global assessment is, however, still recommended. Both endpoints should be evaluated as responder rates. The numerical evaluation of changes in scales is regarded to be a secondary endpoint. As per EMEA Guidance on The Evaluation of Medicinal Products for the Treatment of IBS, a responder has to demonstrate abdominal pain score which has improved at least 30% compared to baseline. Recent studies also show that there is high placebo response rate in functional bowel disorders which has a negative correlation with duration of study. So to overcome this confusion of high placebo response, this study is designed, unlike previous studies in our country, with a longer study period along with a larger sample size.

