# RESEARCH QUESTION

Is multistrain probiotics with standard treatment more effective at reducing IBS symptoms than standard treatment of IBS?

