#### **MATERIALS AND METHODS**

# a. Study Population:

Diagnosed cases of IBS using Rome III criteria.

Ethnicity - Bangladeshi

Age - 18-55 years

Sex - Male and female

b. Study design: Randomized controlled clinical trial.

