### i. Sample Size:

For our trial, we will take equal sample size for both the groups  $(n_1 = n_2)$ . The sample size is to be determined using the following formula -

Sample size in each group,  $n_1$  = 2  $\sigma^2(Z_\beta + Z\alpha)^2 \, / \, (\mu_1 - \mu_2)^2$ 

Here,

 $Z_{\beta}$ = 0.84 at 80% power

 $Z\alpha = 1.96$  at 95% confidence interval

 $\mu_1$  –  $\mu_2$ = Minimum clinically important difference = 30 %( a minimal clinically significant reduction of 30% is desirable in probiotics group compared to placebo)

 $\sigma$  = Standard deviation = 87.77 (G. Sisson, et al. 2013)

Since there is no such study or trial carried out in Bangladesh, we could not find any reference value of Standard deviation of IBS-QOL or IBS-SSS scale among patients of Bangladesh. Hence we used a recent study (G. Sisson, 2013) to estimate the standard deviation.

The standard deviation found in the G. Sisson, et al. 2013 trial was 13.21 for IBS-QOL scale and 87.77 for IBS-SSL. Our study objectives include both the measures; hence we have considered the higher value of standard deviation so that the sample size is sufficient to cover both objectives.

Sample size in each group,  $n_1 = 2 \times (87.77)^2 \times (0.84 + 1.96)^2 / (30)^2$ 

= 135

Total sample size, n = 270

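### The protocol is titled double-blind and placebo-controlled, but its control arm receives standard treatment only, and the text shown describes no placebo or masking

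*Protocol*

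**What the plan says.** The protocol describes the comparator in two ways.

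**Placebo, blinded**
- Title: "a randomized, double-blind, placebo-controlled clinical trial".
- Section i, Sample Size, explaining the target difference: "a minimal clinically significant reduction of 30% is desirable in probiotics group compared to placebo".

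**Standard treatment alone, blinding not mentioned**
- Abstract: patients are randomized to probiotics "with standard treatment or only standard treatment for 8 weeks".
- Research Question: "Is multistrain probiotics with standard treatment more effective at reducing IBS symptoms than standard treatment of IBS".
- Section b: "Study design: Randomized controlled clinical trial", with neither placebo nor blinding in the description.
- Procedures of preparing and organizing materials, the operative description of the arms: one group takes the capsules with standard treatment, "while the other group will receive only standard treatment for 8 weeks".

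The Procedures section specifies the active product by strain, capsule count and CFU, but describes no placebo counterpart. Section m, Randomization, names the software and nothing else. The remaining mentions of placebo or double-blinding concern earlier trials or the placebo response in general.

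**The concern.** The comparator and the blinding determine what the trial can claim, and they are matters for the protocol itself. A site that follows the Procedures section would run an open-label trial under a double-blind title.

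The outcome makes this serious. Abdominal pain is reported by the patient and scored at monthly interviews. If only one arm takes capsules, patients know which arm they are in, and whether the interviewer knows is not stated. A difference between arms would then contain both the product's effect and the effect of expecting benefit, and the analysis could not separate them.

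The Rationale itself names the hazard: "there is high placebo response rate in functional bowel disorders which has a negative correlation with duration of study". Its answer is a longer study and a larger sample. Neither equalises expectation between an arm with capsules and an arm without, and a larger sample makes a biased difference more likely to reach significance. The Confounding variables section says that other IBS drugs "will be prescribed in both the groups similarly according to the needs of the patients", which guards against unequal co-treatment but not against expectation about the capsules.

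**Working it through.** **1. Comparison of the text.** The finding rests on this step.

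| Place in the protocol | Comparator | Blinding |
|---|---|---|
| Title | placebo | double-blind |
| Section i, Sample Size | placebo | not mentioned |
| Abstract | standard treatment only | not mentioned |
| Research Question | standard treatment | not mentioned |
| Section b, Study design | unspecified control | not mentioned |
| Procedures (arm description) | standard treatment only | not mentioned |
| Section m, Randomization | not mentioned | not mentioned |

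The abstract and the Procedures section both say that controls get only standard treatment. That makes it hard to read an unmentioned placebo into the control arm.

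**2. The plan's own sample size.** Inputs from section i: SD 87.77, difference 30, z-values 0.84 and 1.96.

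- n per group = 2 × 87.77² × (0.84 + 1.96)² / 30² = 134.2; the protocol states 135, or 270 in total.
- Dropout adjustment: 270 / (1 − 0.08 − 0.08)² = 382.7; the protocol states 384 and rounds to 400, or 200 per arm.

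The sample size reproduces closely. It would be the same with a placebo or an open control, so the conflict changes no planned number, only what the result means.

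**3. Illustration: how easily an expectation effect could pass for a treatment effect.** The protocol gives no size for such an effect, so every expectation difference below is assumed, and the true probiotic effect is set to zero.

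*Score scale.* 200 per arm, unpaired t-test, two-sided 0.05, with 87.77 taken as the SD of the compared IBS-SSS total.

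- Standard error = 87.77 × √(2/200) = 8.777.
- Smallest significant difference = t(0.975; 398 df) × 8.777 = 1.966 × 8.777 = 17.26 points. At 184 per arm (200 less 8%) it is 17.99.
- Probability of a significant result, from the noncentral t distribution:

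| Assumed expectation difference | 200 per arm | 184 per arm |
|---|---|---|
| 5 points | 8.8% | 8.5% |
| 10 points | 20.6% | 19.3% |
| 20 points | 62.3% | 58.7% |

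*Responder scale.* 184 per arm, two-proportion test with pooled variance under the null, normal approximation. The control response is also assumed.

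| Assumed control response | +5 percentage points | +10 | +15 |
|---|---|---|---|
| 30% | 17.6% | 52.0% | 84.7% |
| 40% | 16.2% | 48.7% | 82.4% |
| 50% | 16.0% | 48.7% | 83.2% |

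Without an expectation difference, each probability would be about 5%.

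**The case against.** The conflict between the title and the arm description cannot be argued away, but four objections deserve an answer.

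**The numbers do not measure the defect.** This largely stands. A critical difference below the design difference of 30 is what any trial with 80% power has; at 135 per arm it is 21.0. It would be the same with a perfect placebo. The expectation effects are assumed, so the percentages show only how sensitive a trial of this size is to a bias of a given size. The score-scale figures also use the SD of the IBS-SSS total, whereas the primary variable is abdominal pain, for which the protocol gives no SD. The finding does not depend on these figures.

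**An open add-on comparison is legitimate.** True: it answers the Research Question as worded. If that is the intended design, the error lies in the labels in the title and section i, and expectation bias becomes a limitation to state. But the title's claim must then be dropped.

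**Some pages and figures are not available.** A description of placebo or masking could be among them, so the absence can be asserted only for the text shown. The title and section i would still contradict the abstract, the Research Question and the Procedures section.

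**The blank group line on the data sheet proves nothing.** It could hold a masked code. That is fair; it matters only if blinding is claimed, and then the protocol should say what is entered there.

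**Conclusion.** The concern holds and must be fixed. The protocol states two incompatible designs: blinded against placebo in the title (with placebo repeated in section i), and standard treatment alone as control in the abstract, the Research Question and the arm description. As the arms are written, the trial can support a conclusion about adding capsules to standard treatment, but not a placebo-controlled, probiotic-specific one.

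The contradiction is certain because it rests on the protocol's own text. That patients would know their arm follows from reading the arm description literally. The size of the resulting bias is unknown. Under the assumptions in the illustration, even a difference below the planned 30 points could give a significant result often: about 9%, 21% and 62% of the time for 5, 10 and 20 points.

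**What to change.** Decide which design is meant and make the title, Abstract, Research Question, section i and the Procedures section agree. The sponsor must choose; there are two consistent ways to do it.

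- **If placebo is intended:** state matching placebo plus standard treatment for the control arm in the Abstract, Research Question and Procedures section. State who is blinded: patient, interviewer, dispenser. Bring sections b and m into line. Say that the group line on the data sheet in Appendix I holds only a masked code, or keep it off the sheet.
- **If placebo is not intended:** remove the double-blind and placebo-controlled labels from the title and the reference to placebo from section i. Limit the conclusion to an open-label add-on comparison, name expectation as a limitation, and state whether the interviewer is masked.

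The second route costs only text changes and a weaker design label. The first also needs text changes and, if no placebo was planned, the cost of supplying one. The Ethical Consideration section says the protocol already has committee approval, so a change to the title or the arms amends approved text. The sample size need not change on this account.
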